### 3.9.3 Subgroup analysis

Subgroup analysis of the primary efficacy endpoint will be conducted based on the following factors (m-ITT set):

- (1) Age
- (2) Sex
- (3) Medication history
- (4) Pre-stroke mRS score
- (5) Baseline stroke severity (NIHSS score)
- (6) Blood glucose level at admission
- (7) Baseline infarct size (PC-ASPECTS score and quantitative measurement)
- (8) Baseline collateral circulation status (PC-CS and BATMAN scores)
- (9) Stroke etiology
- (10) Location of basilar artery occlusion
- (11) Time from symptom onset to randomization

- (12) Time from randomization to groin puncture
- (13) Time from randomization to guiding catheter insertion into the vascular puncture sheath
- (14) Time from randomization to cerebrovascular reperfusion

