Does IVT before EVT achieve higher recanalization rates? A retrospective study^[20] including 93 AIS patients with middle cerebral artery occlusion showed that IVT with EVT resulted in a higher proportion of reperfusion within 1 hour of femoral artery puncture compared to only EVT. Moreover, IVT with EVT achieved significantly higher rates of successful reperfusion (mTICI \geq 2b). The DIRECT-MT study^[17] found that IVT with EVT caused fewer new infarctions from thrombus fragmentation than only EVT. Similarly, post-hoc analyses of the ESCAPE trial^[21] demonstrated that IVT with EVT significantly reduced new infarct risk compared to only EVT. Another study of 57 patients with M1 segment occlusions^[22] reported that IVT with EVT often required fewer thrombectomy passes to achieve recanalization compared to only EVT.

Combination therapy combines the rapidity of IVT with the high recanalization rates of EVT, theoretically offering better outcomes than only EVT. However, most of these studies focus on anterior circulation stroke treatment. To date, no large-scale RCTs have specifically evaluated EVT with or without prior IVT for AIS-BAO. Therefore, we plan to conduct a multicenter, prospective, randomized controlled study to assess the impact of different EVT strategies on outcomes in AIS-BAO.

2. Study objectives

The primary objective of this trial is to compare the efficacy and safety of IVT followed by EVT versus EVT alone in patients with AIS caused by BAO who are eligible for both treatment strategies within 4.5 hours after symptom onset.

The secondary objectives include assessing the effects of the two treatment strategies on neurological function (assessed by National Institutes of Health Stroke Scale [NIHSS] score), activities of daily living (assessed by Barthel Index [BI] score), quality of life (assessed by EQ-5D-5L score), cerebrovascular reperfusion (assessed by

eTICI), cerebrovascular recanalization (assessed by mAOL), infarct size (assessed by PC-ASPECTS and quantitative imaging detection), mortality, and the incidence of symptomatic intracranial hemorrhage (sICH).

3. Study design

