5.1 Study treatment

Patients in the IVT followed by EVT group will receive IVT with rtPA (0.9 mg/kg, maximum 90 mg in one hour), which is followed by EVT. Patients in the EVT alone group will not receive IVT and will undergo EVT alone.

Note: The efforts should be made to minimize delays in EVT initiation caused by IVT procedure in the IVT followed by EVT group. For patients undergoing screening evaluation by CTA or MRA, the time from randomization to femoral artery puncture should be as short as possible, with all patients aiming to achieve a median time of 60 minutes or less from randomization to groin puncture and prompt completion of the guiding catheter inserting into the vascular puncture sheath. For patients undergoing screening evaluation by DSA, the guiding catheter insertion into the vascular puncture sheath should be completed as quickly as possible after randomization according to the assigned treatment strategy. We will record and compare the time from onset to door, from onset to screening imaging, from last non-invasive imaging to groin puncture in the DSA randomized patients, from onset to randomization, from hospital admission to IVT, from hospital admission to groin puncture, from hospital admission to guiding catheter inserted into vascular puncture sheath, from randomization to IVT, from randomization to groin puncture, from randomization to guiding catheter inserted into vascular puncture sheath, and from randomization to cerebrovascular reperfusion/recanalization between the two groups

In this trial, the initiation time of EVT procedure is defined as the moment the guiding catheter is inserted into the vascular puncture sheath in preparation for subsequent therapeutic procedures which may include retrievable stent thrombectomy, thrombus aspiration, balloon angioplasty, stent implantation, or combinations thereof. The end time of EVT procedure is defined as the moment all devices in the vascular puncture sheath are removed (regardless of whether the vascular puncture sheath is retained for a short period of time). The specific EVT approach for each patient will be determined by the treatment team based on the individual's clinical condition. Vascular imaging processes conducted before EVT initiation, including CTA, MRA, and DSA, are all considered vascular screening procedures during the screening phase.

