10.3 Subgroup analyses

Subgroup analyses of the primary endpoint will be conducted based on the following variables:

- (1) Age
- (2) Sex
- (3) Medication history
- (4) Pre-stroke mRS score
- (5) Baseline stroke severity (NIHSS score)
- (6) Blood glucose level at admission
- (7) Baseline infarct size (PC-ASPECTS score and quantitative measurement)
- (8) Baseline collateral circulation status (PC-CS and BATMAN scores)
- (9) Stroke etiology
- (10) Location of basilar artery occlusion
- (11) Time from symptom onset to randomization
- (12) Time from randomization to groin puncture
- (13) Time from randomization to guiding catheter insertion into the vascular puncture sheath
- (14) Time from randomization to cerebrovascular reperfusion

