#### 2.1.2 Secondary endpoints

The secondary endpoints are as following:

- (1) Proportions of patients with mRS = 0 or 1 at 90 days after stroke onset.
- (2) Proportions of patients with mRS = 0–3 at 90 days after stroke onset.
- (3) mRS score at 90 days after stroke onset.
- (4) NIHSS score at 18–24 hours after procedure, 24–74 hours after procedure, and 5–7 days after stroke onset and their changes from baseline.
- (5) Proportions of patients with a NIHSS score = 0 or 1, a NIHSS score = 0–2, a NIHSS score improvement  $\geq 4$  points, and a NIHSS score improvement  $\geq 8$  points at 18–24 hours after procedure, 24–74 hours after procedure, and 5–7 days after stroke onset.
- (6) Glasgow coma scale score (GCS) at 18–24 hours after procedure, 24–74 hours after procedure, and 5–7 days after stroke onset and their changes from baseline.
- (7) Barthel Index score (BI) and proportions of patients with BI = 95–100 at 30 and 90 days after stroke onset.
- (8) EQ-5D-5L score at 90 days after stroke onset.
- (9) eTICI score and successful reperfusion rates before and after EVT.
- (10) mAOL score and recanalization rates at 24–72 hours after procedure.
- (11) PC-ASPECTS score at 24–72 hours after procedure and 5–7 days after stroke onset.
- (12) Lesion volume based on quantitative imaging detection at 24–72 hours after procedure and 5–7 days after stroke onset.

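### Subgroup items 12–14 are times measured after randomisation that IVT can change, so treatment differences within their strata are not randomised comparisons

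*SAP*

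**What the plan says.** SAP 3.9.3 opens with "Subgroup analysis of the primary efficacy endpoint will be conducted based on the following factors (m-ITT set" and lists 14 factors. Protocol 10.3 has the same list under "Subgroup analyses of the primary endpoint will be conducted based on the following variables". Items 12 to 14 are:

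- "Time from randomization to groin puncture"
- "Time from randomization to guiding catheter insertion into the vascular puncture sheath"
- "Time from randomization to cerebrovascular reperfusion"

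Item 11, onset to randomisation, is the only other time factor, and it ends at randomisation.

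Elsewhere the documents treat the three times as things that allocation can influence. Protocol 5.1 says "The efforts should be made to minimize delays in EVT initiation caused by IVT procedure in the IVT followed by EVT group", and both 5.1 and Appendix 19 plan to compare these times between the groups. The protocol's introduction cites an anterior-circulation study in which "IVT with EVT resulted in a higher proportion of reperfusion within 1 hour of femoral artery puncture compared to only EVT". SAP 2.1.2 makes "eTICI score and successful reperfusion rates before and after EVT" a secondary endpoint.

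Neither list gives cut-points or an interaction test, marks items 12–14 as non-randomised, or says how to place a patient who never reperfuses.

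**The concern.** A subgroup estimate keeps the protection of randomisation only if treatment could not have altered who falls into the subgroup. If IVT delays puncture, the IVT patients still in the fast stratum are those who were quick despite the delay. The slow stratum gains IVT patients who would have been fast without it. If speed also tracks prognosis, through severity, vascular access or site efficiency, the arms are unbalanced within each stratum although they are balanced overall.

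Item 14 goes further. Reperfusion lies on the treatment pathway and its time exists only for patients who reperfuse, so the analysis also selects on an outcome. At stake is how these subgroup displays are read, not the trial's main result.

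**Working it through.** **1. Trial size used.** The plan's figures reproduce.
- Superiority: (1.960 + 0.842)² × (0.4203 × 0.5797 + 0.2614 × 0.7386) / 0.1589² = 7.849 × 0.4367 / 0.02525 ≈ 136 per group; 136 / 0.8 = 170.
- Non-inferiority: 7.849 × 2 × 0.4203 × 0.5797 / 0.15² ≈ 170 per group.

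The concern does not depend on these. They supply the 170 per arm and the 42.03% rate used below.

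**2. Model with no treatment effect in any patient.**
- Prognosis U is standard normal. The log-odds of mRS ≤2 are a − βU, with a set so that both arms average 42.03%.
- Time in SD units is T = ρU + √(1 − ρ²)·e + s for IVT patients, without s for EVT alone (e is standard normal). Every IVT patient is shifted by the same s.
- Strata are split at the pooled median, which is s/2.
- P(fast | U) = Φ((s/2 − s·arm − ρU) / √(1 − ρ²)), with arm = 1 for IVT and 0 for EVT alone. A stratum's success rate is the average of P(mRS ≤2 | U), weighted by the chance of being in that stratum.

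The values of ρ, β and s are assumptions. Shifts of 0.33 and 0.67 SD correspond, for example, to 5 and 10 minutes against an SD of 15 minutes.

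**3. Results at β = 1.0, by numerical integration (IVT minus EVT alone, points).**

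| Shift s | ρ | Fast | Slow |
|---|---|---|---|
| 0 | any | 0.0 | 0.0 |
| 0.33 | 0.3 | +1.3 | +1.3 |
| 0.33 | 0.6 | +2.7 | +2.5 |
| 0.67 | 0.3 | +2.6 | +2.5 |
| 0.67 | 0.6 | +5.5 | +5.0 |

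In the last row, 36.9% of IVT and 63.1% of EVT-alone patients are fast. Success is 54.8% against 49.3% in the fast stratum and 34.6% against 29.6% in the slow one. Overall, IVT has 0.369 × 54.8 + 0.631 × 34.6 ≈ 42.0% and EVT alone has 0.631 × 49.3 + 0.369 × 29.6 ≈ 42.0%. The overall difference is zero although both strata appear to favour IVT.

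**4. Simulated trials, 170 per arm, 3,000 per setting, two-sided 0.05 test in each stratum.**

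| ρ, β | s | Fast / slow (points) | False positives per stratum |
|---|---|---|---|
| 0.3, 1.0 | 0.5 | +2.1 / +1.9 | about 6.5% |
| 0.5, 1.5 | 0.5 | +4.6 / +4.0 | about 10% |
| 0.5, 1.5 | −0.5 | −4.2 / −3.8 | 9–10% |
| all three links tried | 0 | −0.2 to +0.2 | 5.1–5.6% |

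The overall difference stayed within 0.2 points of zero. A stronger link and larger shift (ρ 0.7, β 2.0, s 1.0) give +14.9 / +12.6, but nothing in the documents points to values that large.

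**5. Effect modification.** The fast–slow gap is 5.5 − 5.0 = 0.5 points in the last row of step 3. Over correlations of 0.3 to 0.7 and shifts of 0 to 1 SD, it was at most 2.4 points, and an interaction test rejected in 5–6% of null trials.

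**6. Limit of step 5.** The near-equal sizes come from the uniform shift. Take two equal types with success 60% and 24.06%. Under EVT alone 80% and 20% of them are fast; suppose IVT speeds up 10% of the slow poor-prognosis patients only.
- Fast: (0.80 × 60 + 0.28 × 24.06) / 1.08 = 50.7% against 52.8%, or −2.1 points.
- Slow: (0.20 × 60 + 0.72 × 24.06) / 0.92 = 31.9% against 31.25%, or +0.6 points.

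**The case against.** The bias needs IVT to move these times, and for puncture time the documents lean the other way. The protocol's introduction cites two anterior-circulation trials with no significant difference between strategies in randomisation-to-puncture time, and protocol 5.1 asks sites to keep any delay short. With no shift, the calculation gives no bias. This stands: items 12 and 13 may be little affected. It does not cover item 14.

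Nor is item 12 a consequence of allocation in everyone. Patients may be randomised after DSA. Their arterial puncture can then precede randomisation, and protocol 5.1 tracks puncture in them from the last non-invasive imaging instead. This also stands, but it makes item 12 ill-defined for those patients rather than safe.

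A reader might infer that the plan will manufacture effect modification, such as an apparent benefit of IVT only when puncture is fast. A uniform shift does not produce that: the false difference is almost the same in both strata. A selective shift could produce unequal differences (step 6), but the documents give no evidence of one. They also do not say that these subgroups will support a conclusion. Success in SAP 3.9.1 rests on the adjusted risk difference alone, and the table shells, which might carry cautionary labels, are not in the text available.

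**Conclusion.** The point holds in a limited form. Three of the 14 listed factors are measured after allocation and can be altered by it, so their within-stratum treatment differences are not randomised comparisons. Under a uniform shift of 0.33 to 0.67 SD, correlation 0.3 to 0.6 and β = 1.0, the false difference is roughly 1 to 6 points in each stratum. A steeper prognostic slope gives more. The sign follows the direction in which IVT moves the time, which the documents do not settle.

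Item 14 is the clearest problem, because its definition depends on a secondary endpoint that IVT may change. That patients who never reperfuse have no value follows from the definition; no rule in either document covers them.

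A reader might also infer that the main result is compromised. It is not: the m-ITT comparison, its error rate and the sample size do not use these factors. The matter should be corrected, but it concerns the interpretation of subgroups only.

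**What to change.** Delete items 12–14 from the lists in protocol 10.3 and SAP 3.9.3, and keep item 11 as the baseline time subgroup. Report the three times by arm as process measures, as protocol 5.1 and Appendix 19 already intend. Add them to SAP 3.8, which at present covers only times from symptom onset. State there how patients randomised after DSA and patients without reperfusion are shown.

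If the sponsor wants to keep the displays, label them as non-randomised and exploratory, and state that they do not support a claim of treatment effect or effect modification.

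The cost is a short edit to both documents and the loss or relabelling of three exploratory displays. No data are lost.

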### 3.10 Safety analysis

Safety analysis will be performed using the SS dataset.

All adverse events (AEs) reported during the clinical trial will be summarized. AEs will be coded using MedDRA and classified by SOC and PT. For incidence rate calculations, if a subject experiences multiple different AEs, they will be counted as one case for the overall incidence rate. If the same AE occurs multiple times in the same subject, the subject will still be counted as one case for the incidence calculation of that AE. For severity analysis, only the most severe occurrence of the same AE in a subject will be included. Additionally, if a subject experiences multiple AEs within the same SOC and PT, they will only be counted once for the incidence rate calculation within that SOC and PT.

The incidence, number of cases, and rate of all safety endpoints will be summarized. Exact Clopper-Pearson 95% CIs will be calculated for incidence rates. Group comparisons will use chi-square tests, continuity-corrected chi-square tests, or Fisher's exact test, as appropriate, with P-values reported. RD and RR with 95% CIs will also be calculated.

Mortality events will be analyzed using Kaplan-Meier methodology, with median survival time and 95% CIs reported. Kaplan-Meier survival curves will be plotted, and group comparisons will use the log-rank test with P-values reported.

A list of all AEs, serious AEs, adverse reactions, and serious adverse reactions (SS dataset) will be provided.

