### 2.2 Safety endpoints

The safety endpoints include:

- (1) All-cause mortality within 7, 30, and 90 days after stroke onset.
- (2) Proportions of patients with intracranial hemorrhage and symptomatic intracranial hemorrhage at 24–72 hours after procedure and 5–7 days after stroke onset.
- (3) Proportions of patients with new regional cerebral embolisms during EVT.
- (4) Proportions of patients with new cerebral infarction at 24–72 hours after procedure and 5–7 days after stroke onset.
- (5) EVT procedure-related complications within 90 days after stroke onset.
- (6) Other serious adverse events within 90 days after stroke onset.

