#### 3.9.1 Primary efficacy endpoint

The primary efficacy endpoint, "the proportion of patients with mRS  $\leq 2$  at 90 days after onset," will be statistically described by treatment group. The 95% confidence intervals (CIs) will be calculated using the exact Clopper-Pearson method. Additionally, a bar chart will be used to display the distribution of mRS scores.

When using a superiority hypothesis test, the specific statistical hypotheses are as follows:

Null hypothesis  $H_0: p_T - p_C \leq 0$

Alternative hypothesis  $H_1: p_T - p_C > 0$

$\alpha = 0.025$  (one side)

If the hypothesis is adjusted to a non-inferiority hypothesis after the interim analysis, the specific statistical hypotheses are as follows:

Null hypothesis  $H_0: p_T - p_C \leq -15\%$

Alternative hypothesis  $H_1: p_T - p_C > -15\%$

$\alpha = 0.025$  (one side)

Here,  $p_T$  represent the proportions of patients with mRS  $\leq 2$  in the IVT followed by EVT and EVT alone groups, respectively.

A log-binomial model will be used, assuming the primary endpoint follows a binomial distribution. A log-link function will be applied, with covariates including age, pre-stroke mRS, time from onset to randomization, stroke severity (NIHSS score), and collateral circulation. Adjusted and unadjusted risk difference (RD) and risk ratio (RR) with their 95% confidence intervals will be reported.

For superiority, if the lower bound of the 95% CI of the adjusted RD  $> 0$ , superiority is established.

For non-inferiority, if the lower bound of the 95% CI of the adjusted RD  $> -15\%$ , non-inferiority is established.

Additionally, Chi-square tests (expected cell count  $\geq 5$ ), continuity-corrected chi-square tests (1 expected cell count between 1 and 5), or Fisher's exact test ( $\geq 1$  expected cell count  $< 5$  or any expected cell count  $< 1$ ) will also be used for group comparisons, and P-values will be reported.

The mRS score used in the primary analysis will be based on centralized assessments. If centralized assessments are missing for certain subjects, local investigator assessments will be used by default. Sensitivity analyses will also use local assessments to evaluate the robustness of the results.

A list of all primary efficacy endpoint data for all visits (m-ITT, AT, PPS sets) will be provided.

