#### 3.9.2 Secondary efficacy endpoints

The secondary efficacy endpoints are as following:

- (1) Proportions of patients with mRS = 0 or 1 at 90 days after stroke onset.
- (2) Proportions of patients with mRS = 0–3 at 90 days after stroke onset.
- (3) mRS score at 90 days after stroke onset.

(4) NIHSS score at 18–24 hours after procedure, 24–74 hours after procedure, and 5–7 days after stroke onset and their changes from baseline.

(5) Proportions of patients with a NIHSS score = 0 or 1, a NIHSS score = 0–2, a NIHSS score improvement  $\geq 4$  points, and a NIHSS score improvement  $\geq 8$  points at 18–24 hours after procedure, 24–74 hours after procedure, and 5–7 days after stroke onset.

(6) Glasgow coma scale score (GCS) at 18–24 hours after procedure, 24–74 hours after procedure, and 5–7 days after stroke onset and their changes from baseline.

(7) Barthel Index score (BI) and proportions of patients with BI = 95–100 at 30 and 90 days after stroke onset.

(8) EQ-5D-5L score at 90 days after stroke onset.

(9) eTICI score and successful reperfusion rates before and after EVT.

(10) mAOL score and recanalization rates at 24–72 hours after procedure.

(11) PC-ASPECTS score at 24–72 hours after procedure and 5–7 days after stroke onset.

(12) Lesion volume based on quantitative imaging detection at 24–72 hours after procedure and 5–7 days after stroke onset.

For categorical endpoints (1, 2, 5, 7, 9, and 10), proportions will be calculated with 95% CI using the exact Clopper-Pearson method. Group comparisons will use chi-square tests, continuity-corrected chi-square tests, or Fisher's exact test, as appropriate, and P-values will be reported. RD and RR with 95% CIs will also be calculated. Both unadjusted and adjusted results will be reported. Covariates include age, pre-stroke mRS, time from onset to randomization, NIHSS score, and collateral circulation.

For continuous endpoints (4, 6, 7, 8, 11, and 12), group comparisons will use independent samples t-tests (if normality and homogeneity of variance are satisfied) or Wilcoxon rank-sum tests (if not). Mean differences with 95% CIs will also be calculated. Both unadjusted and adjusted results will be reported. Covariates include age, pre-stroke mRS, time from onset to randomization, NIHSS score, and collateral circulation.

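### Mortality is analysed only without covariate adjustment, in a safety set grouped by treatment received, although five baseline covariates are used for every efficacy endpoint

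*SAP*

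**What the plan says.** SAP 2.2 lists "All-cause mortality within 7, 30, and 90 days after stroke onset" as the first safety endpoint, and Protocol 2 names mortality among the secondary objectives.

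SAP 3.10 analyses safety endpoints in the safety set (SS). For comparisons it states "Group comparisons will use chi-square tests, continuity-corrected chi-square tests, or Fisher's exact test, as appropriate, with P-values reported". The next sentence adds "RD and RR with 95% CIs will also be calculated", with no mention of adjustment. For time to death it states "Mortality events will be analyzed using Kaplan-Meier methodology, with median survival time and 95% CIs reported", then curves, and "group comparisons will use the log-rank test with P-values reported". No covariate, regression model or hazard ratio for death appears there or in Protocol 10.2. SAP 3.2.2 has the SS analysed by the intervention actually received, not by the randomised arm.

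The efficacy sections differ. SAP 3.9.1 fits the primary endpoint "with covariates including age, pre-stroke mRS, time from onset to randomization, stroke severity (NIHSS score), and collateral circulation". SAP 3.9.2 covers the categorical, continuous and ordinal secondary endpoints, twelve in all, and for each type states "Both unadjusted and adjusted results will be reported" and "Covariates include age, pre-stroke mRS, time from onset to randomization, NIHSS score, and collateral circulation". Protocol 8.1.4 has all five variables recorded at baseline.

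**The concern.** The plan treats five baseline variables as worth adjusting for in 90-day functional outcome, where death is the worst category (mRS 6), but drops them when death is analysed by itself. No reason is given. With 170 patients per arm a crude mortality difference has a wide interval, and adjustment would narrow it using data already in hand.

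Two further features of SAP 3.10 bear on this. Grouping by treatment received means that the planned mortality comparison is not strictly a comparison of randomised arms. And the only named numerical summary from the Kaplan-Meier analysis is a median, which exists only if about half of an arm dies within the 90 days of follow-up.

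**Working it through.** **1. The plan's own figure.** The documents give no expected mortality, number of deaths or power for mortality. The only stated calculation is for the primary endpoint (Protocol 10.1, SAP 1.5): 42.03% against 26.14%, one-sided 0.025, 80% power.

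n per group = (1.960 + 0.842)² × (0.4203 × 0.5797 + 0.2614 × 0.7386) / (0.4203 − 0.2614)² = 136

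136 / 0.80 = 170 per group, 340 in total. The stated size reproduces, and 170 per arm is used below.

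**2. Crude precision at an assumed 35% mortality in both arms.** SE of the RD = √(2 × 0.35 × 0.65 / 170) = 5.2 points. The 95% half-width is 1.96 × 5.17 = 10.1 points.

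**3. Gain from adjustment (assumed inputs).** The simulation used 1,500 trials per setting, 170 randomised patients per arm, and death following a logistic model in one normally distributed baseline score. The adjusted RD is standardised: fit a logistic model with arm and score, predict each patient's risk under each arm, and average the difference. AUC is the chance that a patient who dies has a worse baseline score than one who survives. Reduction in the variance of the RD:

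| Mortality | AUC 0.70 | AUC 0.74 | AUC 0.79 |
|---|---|---|---|
| 25% | 9.6% | 15.8% | 23.2% |
| 35% | 14.0% | 15.7% | 21.7% |
| 45% | 12.4% | 19.9% | 22.5% |

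The range is about 10% to 23%. In patients, 340 × (1/0.904 − 1) = 36 and 340 × (1/0.768 − 1) = 103. At 35% mortality the half-width becomes 10.1 × √0.860 = 9.4 points (AUC 0.70) or 10.1 × √0.783 = 8.9 points (AUC 0.79), so about 9 to 9.5.

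**4. Second simulation, other settings.** 2,000 trials, 170 per arm, mortality 40% against 30%, two-sided 0.05. Crude power is about 49%. Adjusted power is 55%, 57% and 63% at AUC 0.68, 0.74 and 0.81. The crude variance is 1.09, 1.18 and 1.39 times the adjusted one, that is, reductions of 8%, 15% and 28% (1 − 1/ratio). Type I error of the adjusted test was 4.5% to 4.9%. The two simulations agree.

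**5. Is the median reached?** With complete follow-up, an arm of 170 reaches its median by day 90 only if at least 85 patients die. Binomial probability by true 90-day mortality:

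| Mortality | 170 in the arm | 136 in the arm |
|---|---|---|
| 35% | <0.1% | <0.1% |
| 40% | 0.5% | 1.2% |
| 45% | 11% | 14% |
| 50% | 53% | 53% |
| 55% | 92% | 90% |

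The planning rates only cap mortality, at 100 − 42.03 = 57.97% with IVT and 100 − 26.14 = 73.86% without. A median would need deaths to make up 0.50/0.5797 = 86% of poor outcomes in the first arm, or 0.50/0.7386 = 68% in the second.

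**6. Grouping.** Protocol 5.3 lets some EVT-alone patients receive IVT after failed reperfusion. SAP 3.1.5 and 3.2.2 do not say which group such a patient joins in the SS. If patients change group for reasons linked to prognosis, the crude SS comparison can be confounded. The documents give no crossover rate, so this cannot be sized.

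**The case against.** The best reply is that nothing in SAP 3.10 is invalid. An unadjusted comparison of randomised arms is unbiased, and chance imbalance in age or NIHSS is ordinary sampling error that the crude interval already covers. The gain is modest: at 35% mortality the half-width shrinks by about one point or less, and no conclusion is shown to change. Deaths also enter an adjusted analysis already, as mRS 6 in the ordinal model. All of this stands, except that the ordinal model does not isolate mortality and that validity by randomised arm does not extend to a set grouped by treatment received.

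Four stronger readings are tempting and not supported:

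- *That mortality gets only P-values and a median.* Crude RD and RR with 95% intervals, exact intervals for incidence, and Kaplan-Meier curves are all planned.
- *That the median will often be inestimable.* This depends on a mortality rate that the documents do not state. At 50% mortality the median is reached about half the time. An unreached median also loses little, because 90-day incidence and its RD remain.
- *That the five covariates are strong predictors of death.* No document quantifies this; the AUC values above are assumptions.
- *That mortality is the main safety outcome.* SAP 2.2 lists six safety endpoints without ranking them.

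**Conclusion.** The point holds as a matter of precision and consistency. Every planned mortality analysis is unadjusted and sits in a set grouped by treatment received, while all efficacy endpoints are adjusted for five covariates already collected. By randomised arm, adjustment would cut the variance of the mortality RD by about 10% to 23%. This rests on assumed mortality of 25% to 45%, an assumed AUC of 0.70 to 0.79, a single prognostic score and 170 randomised patients per arm. It does not describe the SS as the plan groups it, so adjusting within the SS would not by itself restore a randomised comparison.

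The median is a minor point: it is unlikely to be reached if 90-day mortality is about 40% or lower, and the documents do not exclude higher mortality. A reader might infer that the planned crude mortality result is biased. The documents show only that it could be, through the grouping, and not that it is.

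**What to change.** In SAP 3.10, before unblinding for the final analysis:

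1. For 30- and 90-day all-cause mortality, add an adjusted RD and RR with 95% CIs, standardised from a logistic model with treatment and the SAP's own five covariates, collaterals included. Analyse by randomised arm in the m-ITT set, the plan's primary efficacy set.
2. Keep the crude results and the SS results by treatment received as supportive.
3. Replace median survival with Kaplan-Meier mortality at 7, 30 and 90 days, with 95% CIs per arm. Keep the curves and the log-rank test.

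The cost is a few lines of SAP text and one more model, with no new data or patients. At the low end of the assumed range, 25% of 340 is 85 deaths. For a model with treatment and five single-parameter covariates that is 85/6, about 14 deaths per coefficient. The change should be specified in advance, since an adjusted mortality analysis added after unblinding would look data-driven.
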